7.2. Investigation Site(s)

7.3. Definition of Completion of the Clinical Investigation

The study will be considered as complete when 20 subjects have been evaluated and a final clinical study report is complete, excluding those who have been withdrawn.

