7.5.4. Subject Classification

Subjects will be classified according to the criteria below:

- **Screened** – Subjects who are assessed for study eligibility, after they have signed the informed consent form (ICF).
- **Enrolled** – Subjects who have met all the inclusion criteria, do not meet any exclusion criteria and have been assigned a subject identification number.
- **Screen Failure** – Subjects who do not meet all the eligibility criteria. (Reason for the subject's ineligibility will be documented on a *Screening and Enrollment Log*).
- **Withdrawn** – Subjects who do not complete the study due to reasons listed below:
 - Subject voluntarily withdrew their consent.
 - Subject was discontinued from study at the discretion of the principal investigator (PI).
- **Completed** – Subjects will be considered complete if an SpO₂ value below 80% is achieved.

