8.3. Screening Phase (Visit 1)

8.3.1. Informed Consent Process

The investigator shall not enroll any subject to participate in the study or consent any subject prior to receiving IRB approval of the ICF. No study related activities will be conducted until consent is signed.

Study staff will discuss the purpose and procedures of the study, risks and benefits, clarify subject's rights and privacy.

The subjects will be provided with enough time to read and understand the informed consent document and their questions will be answered by study staff prior to the subject signing the informed consent form. The research team will emphasize that participation is voluntary.

Once the subjects' questions have been answered and the informed consent is signed and dated, the Principal Investigator or delegate will also sign the informed consent document, approving that the subject will be enrolled in the study. The investigator shall retain the original copy of the informed consent document in each subjects records and provide a copy to the subject.

The point of enrollment is defined as the time at which the assent, consent and/or parental consent is signed and dated. The informed consent will be valid for 45 days from when the informed consent has been fully executed. The subject may withdraw from the study at any time. The subject may withdraw from the study at any time.

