10. STATISTICAL DESIGN AND ANALYSIS

10.1. Slow Desaturation

10.1.1. Sample Size

10.1.1.1. This study will include at least 10 Dark skin pigmentation subjects based on ISO-80601-2-61.

10.1.1.2. This study will include at least 10 Light skin pigmentation subjects based on ISO-80601-2-61.

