10.1.2. Exclusion Criteria

10.1.2.1. Reference device malfunction and/or provides inconsistent SpO₂ value.

10.1.2.2. Data corruption by device failure or data communication problems.

10.1.2.3. Incomplete study or early termination, where the desaturation protocol could not be completed.

10.1.2.4. Discontinuities and abrupt dropouts due to instruments recalibration or device failure.

10.1.2.5. Low signal quality, e.g. due to noise or interference.

10.1.2.6. Subject's oxygen saturation is unstable. This is determined using multiple consecutive SpO₂ values from reference the device, to be stable within 2% SpO₂ (as obtained from a reference device) to include the measurement pair.

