10.2. Fast Desaturation**10.2.1. Sample Size**

10.2.1.1. This study will include at least 10 Dark skin pigmentation subjects based on ISO-80601-2-61.

10.2.1.2. This study will include at least 10 Light skin pigmentation subjects based on ISO-80601-2-61.

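### Does the completion count of 20 in section 7.3 let the study end short of its 10 dark and 10 light subjects?

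*Combined protocol and SAP*

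**What the plan says.** Section 7.3 defines completion of the investigation: "The study will be considered as complete when 20 subjects have been evaluated". The same sentence adds a second condition, a completed final clinical study report, and leaves withdrawn subjects out of the count.

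Section 10 sets the minimums separately for each analysis. For slow desaturation, section 10.1.1 states "This study will include at least 10 Dark skin pigmentation subjects based on ISO-80601-2-61", with a matching line for light skin. For fast desaturation, section 10.2.1 states "This study will include at least 10 Light skin pigmentation subjects based on ISO-80601-2-61", with a matching line for dark skin. Section 7.5.3 caps enrolment at 40.

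Section 7.5.4 gives two grounds for the class *Withdrawn*: the subject withdrew consent, or the investigator discontinued the subject. A subject is *Completed* once an SpO₂ "value below 80% is achieved". *Evaluated* is not among the defined classes.

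Two of the analysis exclusions act on whole subjects. Item 10.1.2.3 removes from the slow analysis "Incomplete study or early termination, where the desaturation protocol could not be completed". Item 10.2.2.4 removes from the fast analysis anyone with no valid event at a reference SpO₂ of 92% or lower.

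**The concern.** The number in 7.3 is the bare sum of the two skin-group minimums, yet 7.3 names neither skin group, neither desaturation condition, and no requirement that the data be usable. It drops only withdrawn subjects, whereas section 10 drops others too. The clearest case is a subject who finishes the visit but has no valid fast event. That subject is not withdrawn, so on a plain reading counts toward the 20, yet is missing from the fast analysis.

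Reading *evaluated* as *Completed* does not remove the mismatch. A subject can fall below 80% in the slow run, be classed as complete, and still have no valid fast event.

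The 10 + 10 figure is the only sample-size basis in the visible text. If the study ended at exactly 20 with one such loss, one analysis would hold 9 usable subjects in a skin group.

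**Working it through.** **Reproducing the plan's figure.** 10 dark (10.1.1.1, 10.2.1.1) + 10 light (10.1.1.2, 10.2.1.2) = 20, the count in 7.3. The documents give no power calculation, standard deviation, margin or expected loss rate, so there is no other figure to reproduce.

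**How exposed an exact 10 + 10 would be.** Suppose the study stopped at exactly 10 + 10 and the minimums were counted after exclusions. If each subject is lost from one analysis independently with probability *p*, the chance that nobody is lost is (1 − *p*)^20. The values of *p* are assumptions.

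| Assumed *p* | (1 − *p*)^20 | Mean number desaturated to retain 20, 20/(1 − *p*) |
|---|---|---|
| 2% | 0.668 | 20.4 |
| 5% | 0.358 | 21.1 |
| 10% | 0.122 | 22.2 |
| 20% | 0.012 | 25.0 |

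The last column assumes each lost subject is replaced from the same skin group and that a loss affects both analyses alike. If losses in the two analyses are independent, the simulated means are 20.7, 21.8, 23.4 and 26.9. On either assumption the number desaturated stays within 40 in more than 99.9% of runs.

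**What one loss costs.** The visible accuracy formulas in 10.1.3 pool all subjects. Going from 20 subjects to 19 multiplies a subject-level standard error by √(20/19) = 1.026, a widening of about 2.6%.

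**Does the plan allow stopping short?** Setting the sections side by side:

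- Section 7.3 says when the investigation counts as complete. It does not say that enrolment stops at 20, and completion also needs the report.
- Sections 10.1.1 and 10.2.1 require 10 + 10 for each analysis. Section 8.4.1 lets a subject take part in the slow condition, the fast conditions or both, so one total of 20 cannot stand in for the two per-analysis requirements. Both have to be met.
- Section 8.3.2 classifies subjects as light or dark by colorimeter and provides for a review so that the two groups are equally represented. It gives no count.
- Item 10.1.2.3 largely overlaps with *Withdrawn*: whoever stops by choice or by the investigator's decision is already outside the 20. The clear remaining case is 10.2.2.4. Subjects need a room-air saturation of at least 95% to be eligible (7.5.2), and the procedure goes as low as a 70% target (8.4.1), so nothing in the documents points to losses of 10% to 20%.
- The phrase in section 10 does not say whether the minimums are counted before or after exclusions. If before, an exclusion breaks no minimum.

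**Room under the cap.** This depends on what *enrolled* means. Section 7.5.4 has "Subjects who have met all the inclusion criteria, do not meet any exclusion criteria and have been assigned a subject identification number"; section 8.3.1 has "The point of enrollment is defined as the time at which the assent, consent and/or parental consent is signed and dated". Under 7.5.4 the room is ample, as above. Under 8.3.1, screen failures use up places. Assume 30% screen failure, shared losses and *p* = 5%, 10% or 20%. If every consenting person belongs to the skin group still needed, the chance of reaching 20 usable subjects within 40 consents is P[Bin(40, 0.7(1 − *p*)) ≥ 20] = 99%, 97% or 82%. If consenting people are a random 50/50 mix, so that each yields a usable dark or light subject with probability 0.35(1 − *p*) apiece, the chance of at least 10 of each is about 80%, 71% or 48%. These figures turn on rates the documents do not give, and they concern the enrolment definition, which is a separate query from 7.3.

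**The case for a change.** The best case for a change is that one clause can declare the study complete while another is unmet. The visible text has no rule on which governs and no replacement rule. The two analyses have different exclusion lists, so even reading *evaluated* as analysable leaves open for which analysis. The pigmentation review is to be done only where applicable and sets no number. The remedy would be cheap: define the term, add a cross-reference, and desaturate perhaps a few more people.

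Much of this stands as description. *Evaluated* is undefined, 7.3 does not point to section 10, and a zero reserve makes an exact 10 + 10 fragile under even small assumed losses. What does not stand is the step to a defect. That excluded subjects count toward the 20 depends on one reading of *evaluated*, and that a minimum is then broken depends on one reading of what it means to include 10 subjects. Two clauses that set different conditions are not in conflict when both can be met, and here they can: meeting section 10 means carrying on beyond 20 where needed, which 7.3 does not forbid. The low cost of the edit does not create a benefit, because no reported result would be computed or interpreted differently.

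**Conclusion.** No change to the plan follows. Section 7.3 leaves a term undefined and lacks a cross-reference, but a study team working from the whole document would fill that gap sensibly: complete 20, check the section 10 minimums for each analysis, and continue within the cap if one is short. No shortfall is shown.

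The effect at stake is small. Losing one subject of 20 widens a subject-level standard error by about 2.6%, and the visible analysis is pooled, with no test, power statement or acceptance limit by skin group. The (1 − *p*)^20 figures show how thin an exact 10 + 10 is, but they rest on assumed loss rates and on counting the minimums after exclusions.

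The conclusion assumes that section 10 is treated as binding. That replacement fits within 40 further assumes that enrolment follows 7.5.4; the difference from 8.3.1 on that point is best raised separately.

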7.4. Study Devices and Comparators

Study Devices and Technologies

- Masimo W1™ – Test
- Apple Watch Series 8 – Test
- RD SET® Adt - Control

FDA-Cleared Safety Equipment

- Capnostream 20
- Nefin bmeye
- ECG Module

Research Equipment (as needed)

- Masimo Pulse Co-Oximeter (Rad-97 or comparable)
- Data Collection Research Equipment (e.g. [REDACTED] Lab Chart, smart phone with data collection application or comparable)
- Colorimeter (e.g., Delfin SkinColorCatch or comparable)
- Warm water bottle, heating pad or Comparable
- [REDACTED]
- Laboratory CO-oximeters/blood analyzers (e.g. Radiometer ABL90 Flex or comparable)

7.5. Subjects

7.5.1. Inclusion Criteria

- Subject is 18 to 55 years of age.
- Subject is American Society Anesthesiologist status 1(ASA1)
- Subject has a BMI between 18 and 35.
- Subject is able to read and communicate in English and understands the study and the risks involved.

7.5.2. Exclusion Criteria (Ineligible Subjects)

- Subject is currently taking any medications which in the opinion of the principal investigator would not be suitable for participation in the study.
- Subject is wearing nail polish that cannot be removed, gel nails, and/or acrylic nails that can interfere with study device's placement.
- Participants with conditions or skin abnormalities at or around site of sensor placement that could affect the placement on the sensor or prevent monitoring of physiological parameters during the study, such as psoriasis, eczema, angioma, scar tissue, burn, fungal infection, substantial skin breakdown.
- Subject has participated in an investigational drug study within one month prior to the start of the study.
- Subject has failed the Allen's Test to confirm patency of the collateral artery.

- Subject is female with a positive pregnancy test, or is female and is unwilling to use effective birth control between the time of screening and study termination.
- Subject has a positive urine cotinine or drug test.
- Subject has a reported allergy to Lidocaine.
- Subject has clinically significant anemia or other hemoglobinopathy.
- Subject has a room air saturation of less than 95% by pulse oximetry.
- Subject has a clinically significant abnormal EKG.
- Subject has a clinically significant abnormal pulmonary function test via spirometry.
- Subject is intolerant to a breathing mask apparatus.
- Subject has a COHb greater than 3%, or MetHb greater than 2%.
- Subject has another condition, which in the opinion of the principal investigator would not be suitable for participation in the study.
- Subject is unwilling or unable to provide informed consent or comply with the study procedures.

7.5.3. Number of Subjects

Up to 40 subjects will be enrolled in the study.

7.5.4. Subject Classification

Subjects will be classified according to the criteria below:

- **Screened** – Subjects who are assessed for study eligibility, after they have signed the informed consent form (ICF).
- **Enrolled** – Subjects who have met all the inclusion criteria, do not meet any exclusion criteria and have been assigned a subject identification number.
- **Screen Failure** – Subjects who do not meet all the eligibility criteria. (Reason for the subject's ineligibility will be documented on a *Screening and Enrollment Log*).
- **Withdrawn** – Subjects who do not complete the study due to reasons listed below:
 - Subject voluntarily withdrew their consent.
 - Subject was discontinued from study at the discretion of the principal investigator (PI).
- **Completed** – Subjects will be considered complete if an SpO₂ value below 80% is achieved.

7.5.5. Study Duration

Expected duration of study enrollment is 1 to 3 months. The expected duration of each subject's participation in the lab will be approximately 6 hours (approx. 2 hours for the screening phase and 4 hours for the data collection phase).

8. STUDY PROCEDURES

This study will be conducted in four phases: recruitment phase, screening phase, data collection phase and follow-up phase. Each phase includes one visit; these visits will either be remote or in-person depending on the scheduled activities. Multiple phases/visits may be combined into the same day (as applicable).

8.1. [REDACTED]

[REDACTED]	[REDACTED]	[REDACTED]	[REDACTED]
[REDACTED]	[REDACTED]	[REDACTED]	[REDACTED]
[REDACTED]	[REDACTED]	[REDACTED]	[REDACTED]
[REDACTED]	[REDACTED]	[REDACTED]	[REDACTED]

8.2. Recruitment Phase (Pre-Screening)

Subjects will be recruited using IRB-approved advertisements. Subjects may also be referred to the study by previous subjects. Subjects who are interested in participating will complete an online screening survey via REDcap. At this time interested subjects will have an opportunity to read the IRB-approved Informed Consent Form (ICF). After the screening survey is completed the study staff will review and subjects who qualify based on the survey will be asked to participate in the screening phase and come on-site for Visit 1. Study staff have the option of remotely consenting qualified subjects who have a pre-existing Electronic Medical Record (EMR) at Duke prior to Visit 1. Remote consent will follow the same informed consent process as outlined in Section 8.3.1.

8.3. Screening Phase (Visit 1)

8.3.1. Informed Consent Process

The investigator shall not enroll any subject to participate in the study or consent any subject prior to receiving IRB approval of the ICF. No study related activities will be conducted until consent is signed.

Study staff will discuss the purpose and procedures of the study, risks and benefits, clarify subject's rights and privacy.

The subjects will be provided with enough time to read and understand the informed consent document and their questions will be answered by study staff prior to the subject signing the informed consent form. The research team will emphasize that participation is voluntary.

Once the subjects' questions have been answered and the informed consent is signed and dated, the Principal Investigator or delegate will also sign the informed consent document, approving that the subject will be enrolled in the study. The investigator shall retain the original copy of the informed consent document in each subjects records and provide a copy to the subject.

The point of enrollment is defined as the time at which the assent, consent and/or parental consent is signed and dated. The informed consent will be valid for 45 days from when the informed consent has been fully executed. The subject may withdraw from the study at any time. The subject may withdraw from the study at any time.

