To ensure equal representation of light- and dark- skinned subjects, the collected skin pigmentation data will be reviewed where applicable to ensure recruited subjects represents adequate spread for both light- and dark-skin groups and are not concentrated near the ITA cutoff of 10.

Sensor site screening: Sensor application sites (e.g., wrist) will be screened for tattoos. Tattoos near the sensor site will be documented in the case report form. Subjects that have a tattoo(s) in the area of device placement may be disqualified; per PI and/or study staff discretion.

Physical examination: Including height, weight, calculated Body-Mass Index (BMI), and Allen's test. A directed physical examination with focus on cardiovascular and respiratory systems with airway examination and a focused neurological and musculoskeletal examination will be performed and assessed. Reported outcome as either WNL, NCS, or CS (within normal limits, not clinically significant or clinically significant). Comments added if NCS or CS to explain selection in Case Report Form (CRF).

Vitals: Vital signs, such as blood pressure and heart rate, will be recorded for subject safety monitoring. Pulse oximetry measurements, such as SpO₂, SpCO, and SpHb, may also be recorded.

EKG: A 12-Lead EKG will be completed and reviewed by the Principal Investigator or delegate, if the subject has a clinically significant abnormal EKG the subject will be disqualified.

Pulmonary function test (PFT) assessment: PFT via Spirometry will be completed and reviewed by the Principal Investigator or delegate, if the subject has a clinically significant abnormal PFT the subject will be disqualified.

Venous Blood Samples: Blood samples will be taken (approximately 15 cc). One blood sample will be analyzed via co-oximeter for carboxyhemoglobin (COHb)/methemoglobin (MetHb) levels. The local laboratory will assess the hemoglobin electrophoresis sample to screen out any hemoglobinopathies, which may take up to 72 hours for analysis.

Urine samples: Urine drug screening to test for the presence of drugs such as amphetamines, barbiturates, benzodiazepines, marijuana, and opiates. and cotinine tests. Adult female subjects will be required to take a pregnancy test. Results will be noted. If the pregnancy test is positive, the subject will be removed from the study and notified of their pregnancy test results.

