8.4. Data Collection Phase (Visit 2)

8.4.1. Desaturation General

If accepted into the study, standard noninvasive monitors may be placed on the subject, which may include FDA-cleared pulse oximeters, ECG, and blood pressure cuff(s). This is assessed for subject monitoring only. Blood pressure may be obtained from arm cuffs, leg cuffs, finger cuffs, or equivalent devices.

Transient increases in blood pressure and heart rate can be expected during line placement, needle sticks, blood draws, etc. and may also be attributed to anxiety/nervousness relating to a new environment. In the case where heart rate and blood pressure

changes suggest participant discomfort or a potential safety concern, the participant will be removed from the study after qualifying, according to the discretion of medical and study staff.

A peripheral venous line may be placed in the subject's hand or arm for safety purposes. This line may be used for a qualifying blood draw to verify that the participant meets inclusion criteria.

Local anesthetics such as Lidocaine may be used in the event that an IV is placed to numb the site. Subjects will be given the option to have lidocaine be used during IV placement for the purpose of making catheter placement more comfortable.

The subject will be lying-in a supine position and should refrain from excessive movement during the study.

Masimo W1™ and Apple Watch Series 8 will be placed, per the manufacturer's instructions, on the subject's wrist(s) along with at least one FDA-cleared RD SET Adt which may be covered with an ambient light shield. Sensors may be repositioned, as needed, to ensure proper placement. The site of sensor placement should be assessed throughout the duration of the study. If there are any signs of loss of skin integrity and/or loss of circulation or perfusion, the device should be repositioned.

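### Do two definitions of enrollment (consent signature in 8.3.1, confirmed eligibility in 7.5.4) leave the 40-subject cap or the analysis undefined?

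*Combined protocol and SAP*

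**What the plan says.** Two sections of the protocol define enrollment. Section 8.3.1 (Informed Consent Process) fixes it at signature: "The point of enrollment is defined as the time at which the assent, consent and/or parental consent is signed and dated". Section 8.3.2 starts the eligibility assessment only after the subject and the investigator or delegate have signed. Section 7.5.4 (Subject Classification) calls consented subjects under assessment screened, and defines the enrolled as "Subjects who have met all the inclusion criteria, do not meet any exclusion criteria and have been assigned a subject identification number".

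Two counts frame the study. Section 7.5.3 sets a ceiling: "Up to 40 subjects will be enrolled in the study". Section 7.3 sets the end: "The study will be considered as complete when 20 subjects have been evaluated", with withdrawn subjects left out. Sections 10.1.1 and 10.2.1 each ask for at least 10 dark-skinned and 10 light-skinned subjects.

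Three other statements bear on eligibility found wanting late:

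- Section 8.4.1, on Visit 2, says of an optional venous line: "This line may be used for a qualifying blood draw to verify that the participant meets inclusion criteria".
- Section 8.3.2 lists a "hemoglobin electrophoresis sample to screen out any hemoglobinopathies, which may take up to 72 hours for analysis".
- Section 7.5.4 defines completion by saturation alone: "Subjects will be considered complete if an SpO₂ value below 80% is achieved".

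**The concern.** A subject who signs consent and then fails screening is enrolled under 8.3.1 and a screen failure, never enrolled, under 7.5.4. The ceiling in 7.5.3 is expressed in that ambiguous unit, so the same conduct could exhaust the 40 places under one reading and sit well inside them under the other. If the consent-based count governed and screen failure were high, the study might reach its ceiling before 20 subjects had been evaluated.

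The Visit 2 draw seems to add to the difficulty, because it allows eligibility to be checked again after a subject has been accepted. A subject found ineligible after desaturation below 80% could then meet the definitions of both screen failure and completed. Section 7.3 removes only withdrawn subjects, and the data exclusions in 10.1.2 and 10.2.2 contain no eligibility item. It would then be unclear whether that subject counts toward the 20 or toward the 10 in a skin group.

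**Working it through.** **1. The plan's own figures.** The two skin-group minimums give 10 + 10 = 20, which matches the completion target in 7.3. The documents give no derivation of 40. Set against the target, it allows a loss of 1 − 20/40 = 50%.

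**2. What depends on the definition.** Bias, precision and A_RMS (10.1.3) are sums over pairs of test and reference readings. The no-read rate (10.1.4, 10.2.4) divides by spot checks, and the detection rate (10.2.3) divides by valid fast-desaturation events. None has enrolled subjects as a denominator. A subject who fails screening never reaches device placement and contributes no pairs, spot checks or events. The analysis data are therefore the same under 8.3.1 and 7.5.4. What differs is the number reported as enrolled, the use of the ceiling, and which subjects need a case report form under 11.3.

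**3. The cap under each reading.** Let f be the screen-failure proportion after consent and w the loss after eligibility. Both are assumed, with f from 10% to 50% and w 10% or 20%. Expected evaluated subjects when the ceiling is reached:

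- counted from consent (8.3.1): 40(1 − f)(1 − w)
- counted from eligibility (7.5.4): 40(1 − w)

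| f | w | From consent | Chance of at least 20 | From eligibility |
|---|---|---|---|---|
| 10% | 10% | 32.4 | not run | 36 |
| 20% | 10% | 28.8 | 0.999 | 36 |
| 30% | 20% | 22.4 | 0.822 | 32 |
| 40% | 10% | 21.6 | 0.748 | 36 |
| 40% | 20% | 19.2 | 0.461 | 32 |
| 50% | 10% | 18.0 | 0.316 | 36 |
| 50% | 20% | 16.0 | 0.130 | 32 |

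The chances are upper binomial tails with 40 trials and success probability (1 − f)(1 − w). Counted from eligibility, the chance of at least 20 is about 1.0 at either value of w.

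The consent-based count falls below 20 in expectation when f > 1 − 0.5/(1 − w):

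- w = 10%: 1 − 0.5/0.9 = 0.444
- w = 20%: 1 − 0.5/0.8 = 0.375

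**4. Which reading the text favors.** Section 7.5.4 directly follows the cap in 7.5.3 and is the section that says how subjects are to be classified. Section 7.1 describes enrolled subjects as receiving both watches, which cannot be true of a screen failure. The sentence in 8.3.1 speaks of assent and parental consent, although 7.5.1 admits only adults aged 18 to 55. It reads as carried-over template wording.

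**5. The Visit 2 draw.** The line and the draw are both optional, and a recheck of eligibility is compatible with either definition. The mention of inclusion criteria is a small slip: 7.5.1 contains no blood criterion, while 7.5.2 lists the blood-based ones as exclusions. The 72-hour analysis belongs to the screening sample in 8.3.2, and nothing ties it to the Visit 2 draw. Comparing it with the times in 7.5.5 ("approx. 2 hours for the screening phase and 4 hours for the data collection phase") therefore shows no conflict.

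**6. The subject found ineligible late.** The classes in 7.5.4 are not stated to be exclusive; every completed subject has also been screened and enrolled. A subject found ineligible before completing can be discontinued by the investigator, is then withdrawn, and under 7.3 does not count toward the 20. Only discovery after desaturation below 80% is left open. No visible text permits desaturation with an eligibility result pending, and the table in 8.1 is redacted, so its contents cannot be counted as missing.

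**The case for a change.** The best argument for a change is that a protocol should not define one term in two ways when an operative limit rests on it. The cap, the case report form requirement in 11.3 and the description of the arm in 7.1 all use the word enrolled, and no sentence says which definition prevails. If screen failure were 40% and later loss 10%, the chance of reaching 20 evaluated subjects within 40 consents would be about 0.75, against near certainty when counted from eligibility. The remedy would be wording only and would leave the sample-size target alone.

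The contradiction stands. The consequence largely does not. The shortfall needs rates that the documents do not give, applied to people already filtered by the online survey in 8.2, and it needs the less natural reading of the cap. If the ceiling were reached early, that would be visible during recruitment and could be handled by amendment under Section 12. It would not bias a result.

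It also stands that Section 10 has no rule for a subject found ineligible after data collection. That is a gap, but a narrow one. The subject can be identified in the disposition listing and the analysis shown with and without those readings. The group sizes are minimums and the ceiling leaves room to replace the subject, so a skin group need not end at 9.

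**Conclusion.** No change to the plan follows. Sections 8.3.1 and 7.5.4 do disagree, and 7.5.3 does not name the count it caps, but this is a clerical conflict confined to the ceiling and the disposition counts. The accuracy, no-read and detection measures, the 10 + 10 minimum and the target of 20 are the same under either definition. Choosing one definition in writing would alter no estimate and no conclusion. A report that follows 7.5.4 and gives the numbers consented, failed at screening, eligible, withdrawn and evaluated shows everything a reader needs.

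At most, the consent-based reading gives 16 to 32 evaluated subjects at the ceiling and the eligibility-based reading 32 to 36, with assumed screen failure of 10% to 50% and later loss of 10% to 20%. The conclusion also assumes that subjects who fail screening do not go on to desaturation, as the order of visits in Section 8 implies. It takes no position on which tests belong at which visit. The differing wording in 7.5.4, 8.3.1 and 8.4.1 is for the sponsor and investigator to reconcile as an editorial matter, and the analysis does not wait on it.
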